3.4.2 Baseline Visit and Randomization

Individuals not randomized to receive the orientation session will receive an email invitation to sign up for a baseline visit. All participants will attend a baseline visit, regardless of orientation session assignment. At this baseline visit (~1-1.5 hours), trained study staff will confirm eligibility and describe study procedures. If individuals are interested in participating, study staff will obtain informed consent to assure that they fully understand the demands and purpose of the study before enrolling. Next, study staff will help participants create a Fitbit account and download the Fitbit app. Study staff will then administer a web-based dietary recall, an oral health literacy assessment, and a web-based baseline survey. Once the survey is completed, study staff will mail all participants an e-scale to obtain baseline weight measurement. Once the e-scale is delivered, participants will receive an email that provides information on syncing their e-scale with the Fitbit app, and will be prompted to weigh themselves the following morning using a standardized protocol. Within the week after the baseline visit, a 2nd unannounced web-based dietary recall will be administered, with reminders sent if it is not completed.

Once the weight assessment is completed, participants will be randomized to 1 of 8 experimental conditions via an algorithm on REDCap. Study staff will mail an activity

tracker (Fitbit Inspire 3) within 2 business days to those randomized to the conditions with self-monitoring of steps (i.e., conditions 3, 4, 7, 8; **Figure 2**, above). Once the tracker is delivered, participants will receive instructions for syncing the tracker with the Fitbit app. Study staff will be available to troubleshoot with device syncing, as needed. Then, the weight loss intervention will begin -- participants will receive an automated email describing their assigned intervention.

Following recommendations for factorial designs,³⁵ we will randomize participants to the 8 conditions using restricted randomization. We will stratify by sex assigned at birth and use permuted block randomization with a block size of 8. The allocation sequence was generated using SAS by the study's statistician ([name]) and stored in REDCap. Study staff will use REDCap to implement the random allocation sequence (i.e., randomize a participant) once both the baseline weight and web-based baseline surveys are submitted.

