3.8.2 Secondary and Exploratory Outcomes

Secondary outcomes include the following: 6-month change in caloric intake, physical activity, BMI, and health-related quality of life; 1- and 3-month weight change; and the proportion of participants achieving clinically significant weight loss ($\geq 5\%$ at 6 months). We will also examine additional outcomes: self-monitoring engagement rates and their relation to 6-month weight change; 6-month changes in diet quality; 6-month changes in step count among those assigned to self-monitor steps; the impact of potential moderators on 6-month weight change to determine for whom each self-monitoring strategy works best; and the impact of the orientation session on 6-month retention. In exploratory analyses, 6-month weight change data will be disaggregated by sex.

Caloric intake will be assessed via the Automated Self-Administered 24-hour (ASA24) Dietary Assessment Tool (version 2022 and 2024- beginning in April 2025), which is a free web-based tool developed by the National Cancer Institute.⁴⁹ Participants will be asked to complete a total of four 24-hour dietary recalls, including two at baseline and two at 6 months. At both time points, we will request one weekday recall and one weekend day recall. We will send up to 4 reminders per time point. We will exclude from our analyses any recalls with outliers of daily caloric intake reported as a minimum of <800 kcal for everyone, and a maximum of >4400 kcal for women and >5700 kcal for men, in accordance with ASA24 recommended procedures.⁵⁰ To compute caloric intake at each time point, we will calculate the mean of the weekday recall and the weekend-day recall; if only one recall is available at a given time point, we will use that

value. Diet quality will be assessed using the Healthy-Eating Index-2020,⁵¹ calculated from ASA24 data.

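### Could a second baseline dietary recall completed after the intervention starts be counted as baseline caloric intake?

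*Protocol*

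**What the plan says.** Section 3.4.2 of the protocol sets the order of events. At the baseline visit, "Study staff will then administer a web-based dietary recall, an oral health literacy assessment, and a web-based baseline survey". The e-scale is mailed only after the survey is done, and the participant weighs in on the morning after being notified of delivery. The second recall follows: "Within the week after the baseline visit, a 2nd unannounced web-based dietary recall will be administered, with reminders sent if it is not completed".

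A new paragraph then turns to randomization and gives the trigger twice: "Once the weight assessment is completed, participants will be randomized to 1 of 8 experimental conditions", and, at the end of the section, "once both the baseline weight and web-based baseline surveys are submitted".

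Section 3.8.2 covers handling of the recalls. On chasing: "We will send up to 4 reminders per time point". On exclusion: "We will exclude from our analyses any recalls with outliers of daily caloric intake", with limits in kcal only. On the value analysed: "To compute caloric intake at each time point, we will calculate the mean of the weekday recall and the weekend-day recall", and "if only one recall is available at a given time point, we will use that" value.

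**The concern.** Three features combine. The one-week window governs when the recall goes out, and the reminder limit is a count, so neither gives a last date. Neither trigger statement names the second recall, and section 3.4.2 lists the visit recall apart from the baseline survey. Section 3.8.2 states no exclusion by date.

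Read literally, a participant could be weighed, randomized and started on diet tracking with a calorie goal, then complete the outstanding recall, and have it averaged into baseline. That would lower baseline intake in the diet arms and pull the diet effect on change in caloric intake toward zero. Diet quality comes from the same recalls, and pretreatment caloric intake is a listed moderator, so both would be touched. Conditions with step tracking wait for a tracker to arrive, so exposure to the problem could differ by a randomized factor.

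**Working it through.** The protocol gives no figure on this point, so there is none to reproduce. The check has a reading of the text and an illustration of size.

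**1. What the text implies about order.**
- Section 3.4.2 runs in sequence: visit, scale, weigh-in, second recall, then randomization in a new paragraph.
- The visit has one baseline survey, and the scale is not mailed until it is finished. By the time a weight exists, that survey is already in. A gate of weight plus surveys, in the plural, adds more if it covers something later, and the second recall is the obvious candidate.
- Section 3.9 groups the dietary recall tool with the web-based questionnaires.
- Table 3 places caloric intake at month 0, and section 3.8.2 calls the moderator pretreatment.

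**2. Could the window overlap the start of the intervention?** Assume the scale arrives on day 2, 3, 4, 5 or 7 after the visit, with weighing and randomization the next day. Conditions without steps could then start on day 3, 4, 5, 6 or 8, leaving 5, 4, 3, 2 or 0 days of the 7-day window on or after the start. With 2 days to mail the tracker and an assumed 3 to deliver it, steps conditions have 0 such days in each case. Overlap is possible if the recall is not part of the gate, but this rests on assumed delivery times.

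**3. Size of the bias.** Let f be the share of late second recalls in the diet arms, w the share of the diet effect present by then, and d the diet effect. Baseline is a mean of two recalls, so it moves by f·w·d/2 and the change contrast is attenuated by the fraction f·w/2. For w from 0.5 to 1:
- f = 5%: 1.25% to 2.5%
- f = 10%: 2.5% to 5%
- f = 20%: 5% to 10%

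With d = 300 kcal (assumed) and f = 10%, this is 7.5 to 15 kcal. The standard error of a main effect with all 176 analysed is 2·SD/√176. For an assumed SD of change of 500 to 700 kcal it is 75.4 to 105.5 kcal. The ratio runs from 7.5/105.5 = 0.07 to 15/75.4 = 0.20. Squared, the bias adds about 0.5% to 4% to the mean squared error.

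**4. Cost of a date cut-off at randomization.** If a share f of participants lose the second recall, within-person baseline variance goes from 1/2 to (1 − f)/2 + f = (1 + f)/2 in units of one recall's variance. The 6-month mean keeps 1/2, so the variance of change rises by a factor of at most 1 + f/2. At f = 10% that is 5% in variance and √1.05 = 1.025 in standard error. At f = 20% it is 10% and 1.049.

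**5. Break-even.** The squared bias exceeds this maximum cost when (f·w·d/2)²/SE² > f/2, that is, when f > 2·SE²/(w·d)². With d = 300 and w = 1, the threshold is 2 × 5,682/90,000 = 13% (SD 500) to 2 × 11,136/90,000 = 25% (SD 700). With w = 0.5, it is 51% to 99%.

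**The case for a change.** The strongest case for a change is that visit order and the randomization trigger belong to the protocol, not the SAP, and that section 3.8.2 goes into detail on recalls yet gives no date rule. The same section does fix calendar weeks for step count. The incentive in section 3.3.2 pays for all four recalls whenever completed. A date comparison takes one line of code, and if no recall was late it changes nothing.

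Part of this stands. The gate is not explicit, the two trigger statements differ, and no sentence in the protocol removes a late recall. For a participant whose late recall is the only valid one, the divisor of 2 disappears and the distortion doubles. If early effects were common to all arms (200 kcal) and late shares were 10% with steps and 30% without, the steps contrast would shift by (30% − 10%) × 200/2 = 20 kcal, or 0.19 to 0.27 standard errors on the range above.

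The rest does not carry. The kcal limits are a plausibility filter, and nothing makes them the complete list of reasons to set a recall aside. Rules for assigning a late record to a time point commonly sit in an SAP, and sections 3.10 and 3.11 refer to one that was not available here. The single-recall rule does not show that participants may be randomized without the second recall: it applies at 6 months too and covers recalls dropped as outliers. A cut-off at randomization would also discard clean recalls taken before the intervention began and leave some participants without the weekday and weekend pair.

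**Conclusion.** This is an unwritten detail that a competent analyst fills correctly from the words baseline and pretreatment. The likelier reading of section 3.4.2 already puts the second recall before randomization. To say that a late recall would count as baseline goes further than the text supports.

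If some late recalls were counted, the effect would be confined to change in caloric intake, recall-based diet quality and one moderator. At a 10% late share it is at most 0.20 standard errors on the diet contrast when two recalls are averaged, and it is conservative for that contrast. The upper end needs the full 6-month effect to be present within days. A date cut-off would trade this for a precision loss of similar size. It gains clearly only if late recalls were more frequent than about 13% to 25% with the full effect already present, which nothing in the protocol suggests. The late share, early effect, diet effect and SD are all assumed, so the true size cannot be read from the document.

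Section 6 records that data collection is finished, so the timing of recalls can no longer be altered. The primary outcome rests on a weight taken before randomization and is unaffected. Following the protocol as written leaves the conclusions sound.

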3.4.3 Screen Failures

Participants who consent but then become ineligible prior to randomization will be asked to withdraw from the study and will not be randomized. Examples would include if a participant's baseline weight collected via the study-issued e-scale (after consenting) puts them out of range on the BMI criterion (i.e., no longer being in the 25.0-45.0 kg/m² range), which may occur when their initial BMI that was calculated using self-reported weight put them on the edges of that range), or if a participant reports a pregnancy or exclusionary medical condition in the period between consent and randomization. All other reports of changes to eligibility criteria will be decided upon by study investigators prior to randomization.

3.4.4 Withdrawal/Termination Criteria

If after randomization and during the study period the participant no longer meets certain eligibility criteria, they will be asked to withdraw from the study. This includes the following: if a participant becomes pregnant during the study; finding out that certain criteria were falsified or not reported (e.g., initial age, initial BMI, concurrent enrollment in another weight management intervention, a health condition that contraindicates weight loss or requires more intensive treatment), or investigator discretion for safety reasons.

Participants who become pregnant during the study period will be asked to leave the study. Changes in health behaviors and weight may not be healthy for a baby during pregnancy. Note that if a participant begins use of a weight loss medication / antiobesity medication during the study, they will *not* be asked to withdraw from the study.

3.5 Core Intervention

All participants will receive a 6-month core intervention consisting of the following empirically- and theoretically- supported components:

Fitbit mobile app: Instead of designing our own app, we will leverage an existing state-of-the-art commercial app from Fitbit that is freely available on iPhone and Android platforms. At baseline, participants will install the app. The app will be set up by study staff so that it reflects only the self-monitoring components (tracking diet, steps, and/or weight) to which each participant is assigned. In-app graphical feedback allows participants to view their self-monitoring progress in real time.

Weight loss goal: All participants will receive a goal to achieve 10% weight loss by 6 months, which is consistent with obesity treatment guidelines⁵ and equates to 0.5-2 lbs weight loss/week.

Tailored feedback: Each week, participants in conditions 2-8 will receive an email with tailored feedback pertaining to their progress on their assigned self-monitoring goals (described below). Feedback will be automatically generated using Fitbit data (retrieved from Fitabase) and constructed via Microsoft Office's Mail Merge feature.

Behavioral skills training: Each week, participants will receive an email with theory-informed skills training materials that include structured behavioral lessons on nutrition and physical activity as well as corresponding action plans. These materials will be adapted from our recent trials³⁶⁻³⁷ as well as from gold standard weight loss curricula.³⁸ Lessons include topics such as reading nutrition labels and promoting physical activity. Embedded in this email will be a link to a brief action plan survey (Qualtrics) that incorporates motivational interviewing³⁹⁻⁴⁰ and problem-solving strategies.⁴¹ Specifically, participants will be prompted each week to reflect on their current behaviors and areas for change, generate actionable steps to change, identify confidence in doing so, and brainstorm potential barriers and support people.

3.6 Experimental Intervention Components

Self-monitoring diet (Yes vs. No): Participants randomized to receive this component will be instructed to self-monitor their dietary intake daily via the Fitbit mobile app. This app allows users to track all foods and beverages consumed using a built-in nutritional database, barcode scanner, or manual entry of individual recipes, and to view graphically their change in caloric intake. Participants will receive a tailored daily calorie goal using data reported at baseline: age, sex, weight, and height. For safety, a minimum of 1200 Calories (kcal)/day is set for women and 1500 kcal/day for men.³

Self-monitoring steps (Yes vs. No): Participants randomized to receive this component will be instructed to self-monitor their step count daily via a wrist-worn activity tracker (Fitbit Inspire 3). In conjunction with the self-monitoring goal, a tailored daily step goal will be given (e.g., 7,000 steps) that will adapt based on progress. The initial week's step goal will be based on the participant's baseline scores on the Godin Leisure-Time Exercise Questionnaire (GLTEQ) leisure score index,⁴²⁻⁴³ with scores ranging from 0 to 13 (interpreted as *insufficiently active*) assigned to a goal of 5000 steps per day, scores of 14 to 23 (*moderately active*) assigned to 7000 steps per day, and scores ≥ 24 (*active*) assigned to 10,000 steps per day. Starting in the second week of the intervention, an adaptive step goal will be given using an empirically tested algorithm⁴⁴⁻⁴⁵ whereby the 60th percentile of the past week's daily step counts, rounded up to the nearest multiple of 50, is assigned as the subsequent week's daily step goal. For example, a week with daily steps of 5000, 5100, 6000, 6500, 7000, 8200, and 8500 would result in a daily step goal of 6800 for the subsequent week. The new step goal will appear in each week's progress report. The Fitbit activity tracker will be synced with the Fitbit app to allow participants to view their progress towards the step goal.

Self-monitoring weight (Yes vs. No): Participants randomized to receive this component will be instructed to self-monitor their body weight daily via a Bluetooth enabled e-scale (the Fitbit Aria Air scale). These participants will receive a weekly weight loss goal of 0.5 to 2.0 lbs. (0.23 kg to 0.91 kg) per week, calculated as the magnitude of weight loss that is required to achieve 10% weight loss at 6 months. The e-scale will be synced with the Fitbit mobile app, providing graphical feedback.

3.7 Participant Requirements

Table 2. Participant Time Involvement.

- 10 minute online eligibility screen
- orientation video (~20-25 minutes), if randomized to view it
- baseline visit / informed consent: ~60-90 minutes
- active participation in the intervention: 6 months (~20 minutes of daily tracking of weight-related behaviors, and ~20-30 minutes/week of review of lessons and completion of action plans)
- 4 remote assessments: baseline, 1 month, 3 months, 6 months. The 1-month assessment is expected to be ~5 minutes. The 3 and 6-month assessments are expected to be 30-60 minutes each

3.8 Outcomes

All measures collected are listed in **Table 3**, below.

3.8.1 Primary Outcome

The primary outcome is weight change from baseline to 6 months (in kg), which will be assessed objectively via e-scale (Fitbit Aria Air) that will be mailed to participants. At each assessment, participants will receive an automated email in the morning instructing them to weigh themselves on the e-scale and follow best-practices⁴⁶: place the scale on a hard, flat surface; remove all articles of clothing and accessories; weigh on the scale in the morning before eating or drinking and after emptying their bladder; step on the scale and record the value; and repeat it 2 more times for a total of 3 weight measurements per time point. Weights will sync from the e-scale to the Fitbit app via Bluetooth; as a preventive measure in case of syncing errors, participants will also be asked to input their weight values on a web-based weight check-in form. There is high concordance between weights measured from commercial e-scales and those from scales used in a clinical setting.⁴⁷⁻⁴⁸

3.8.2 Secondary and Exploratory Outcomes

Secondary outcomes include the following: 6-month change in caloric intake, physical activity, BMI, and health-related quality of life; 1- and 3-month weight change; and the proportion of participants achieving clinically significant weight loss ($\geq 5\%$ at 6 months). We will also examine additional outcomes: self-monitoring engagement rates and their relation to 6-month weight change; 6-month changes in diet quality; 6-month changes in step count among those assigned to self-monitor steps; the impact of potential moderators on 6-month weight change to determine for whom each self-monitoring strategy works best; and the impact of the orientation session on 6-month retention. In exploratory analyses, 6-month weight change data will be disaggregated by sex.

Caloric intake will be assessed via the Automated Self-Administered 24-hour (ASA24) Dietary Assessment Tool (version 2022 and 2024- beginning in April 2025), which is a free web-based tool developed by the National Cancer Institute.⁴⁹ Participants will be asked to complete a total of four 24-hour dietary recalls, including two at baseline and two at 6 months. At both time points, we will request one weekday recall and one weekend day recall. We will send up to 4 reminders per time point. We will exclude from our analyses any recalls with outliers of daily caloric intake reported as a minimum of <800 kcal for everyone, and a maximum of >4400 kcal for women and >5700 kcal for men, in accordance with ASA24 recommended procedures.⁵⁰ To compute caloric intake at each time point, we will calculate the mean of the weekday recall and the weekend-day recall; if only one recall is available at a given time point, we will use that

value. Diet quality will be assessed using the Healthy-Eating Index-2020,⁵¹ calculated from ASA24 data.

Physical activity will be assessed via the GLTEQ, a self-report measure that assesses the past week's frequency of different types of exercise (strenuous, moderate, and mild or light) that were engaged in for more than 15 minutes during one's free time.⁴²⁻⁴³ Strenuous activities are described as those where one's "heart beats rapidly" (e.g., running, jogging, or swimming), moderate activities are described as "not exhausting" (e.g., fast walking or tennis), and mild activities are described as requiring "minimal effort" (e.g., yoga or easy walking). A leisure score index will be created using the following formula: (strenuous $\times 9$) + (moderate $\times 5$) + (light $\times 3$), with higher scores indicating more frequent exercise. To assess weekly moderate-to-vigorous physical activity (MVPA), a composite score will be created using the same procedures but excluding the light activities; from this MVPA score index, scores of ≥ 24 units will be interpreted as *active* and scores < 24 will be considered *insufficiently active*.⁵² We will objectively assess step count using the Fitbit Inspire 3 activity tracker, among those assigned to track steps. We will operationalize the week 1 step count as the average of the first 7 days of the intervention and 6-month step count as the average of the last 7 days (week 26), so long as ≥ 3 valid days (≥ 1000 steps/day) per week are reported.⁵³

Health-related quality of life (HRQoL) will be assessed using the 36-item Short Form Health Survey (SF-36),⁵⁴ with scores provided for both the physical component and mental component. It assesses 8 domains: physical functioning, role-physical, bodily pain, general health, vitality, social functioning, role-emotional, and mental health.

Self-monitoring engagement will be assessed objectively for all 182 days (6 months) of the intervention using data collected from the Fitbit digital tools. Engagement will be operationalized as the percent of days in the intervention that participants self-monitor dietary intake, steps, and weight (each reported separately). For self-monitoring of diet, we will count days as valid if they have ≥ 800 kcal recorded, which is a common threshold. For self-monitoring of steps, we will count days as valid only if ≥ 1000 steps are recorded; this minimum threshold is used to minimize the possibility of inaccurately counting days with high amounts of non-wear time.⁵⁵ We will also assess engagement in other intervention components, including the percentage of action plans completed, which is objectively assessed via Qualtrics, with 100% indicating completion of all 19 action plans. Via self-report at 6 months, we will assess which of the 19 lessons were read and the frequency with which progress reports were reviewed, with options of *weekly*, *less than 1 time per week*, *less than 1 time per month*, and *never*.

Putative moderators will be assessed via self-report survey measures administered at baseline, including demographic (e.g., sex, age, education), psychosocial (e.g., stress,

self-efficacy), behavioral (e.g., pretreatment caloric intake and physical activity), and clinical (e.g., type 2 diabetes diagnosis) characteristics. A health literacy questionnaire, the Newest Vital Sign, will be administered orally by study staff at the baseline visit.⁵⁶

Table 3. Assessment Schedule in the Spark Trial.

Construct	Measure or assessment tool	Time Point (months)			
		0	1	3	6
Anthropometric, behavioral, and demographic measures					
Weight (primary outcome)	E-scale (Fitbit Aria Air) ⁴⁶⁻⁴⁸	•	•	•	•
Height	Self-reported ⁵⁷	•			
Caloric intake	ASA24 dietary recall (1 weekday, 1 weekend day) ⁴⁹	•			•
Diet quality	Healthy Eating Index, ⁵¹ measured by ASA24	•			
Physical activity	GLTEQ ⁴²⁻⁴³	•	•	•	•
Physical activity guideline adherence	Stanford Leisure-Time Activity Categorical Item (L-Cat) ⁵⁸	•		•	•
Step count ^a	Activity tracker (Fitbit Inspire 3)	•	•	•	•
History of self-monitoring	Self-reported use of self-monitoring of diet, steps, and weight in the month prior to study enrollment ⁵⁹	•			
Sociodemographic and clinical characteristics	Self-reported age, race/ethnicity, sex, gender, sexual identity, birth country, marital status, education, employment, income, household size, # children in home, prediabetes, type II diabetes, hypertension, smoking	•			
Engagement metrics					
% days of self-monitoring (diet, steps, weight)	Digital tools (Fitbit app, Fitbit Inspire 3 activity tracker, Fitbit Aria Air e-scale, respectively)	•	•	•	•
% action plans completed	Action plans in Qualtrics	•	•	•	•
% lessons read	Self-reported frequency of reading weekly lessons				•
Progress reports viewed	Self-reported frequency of viewing weekly progress reports				•
Psychosocial measures					
Health-related quality of life	SF-36 ⁵⁴	•			•
Self-efficacy for dietary change	Weight Efficacy Lifestyle Questionnaire Short-Form (WEL-SF) ⁶⁰	•		•	•
Self-efficacy for exercise	Exercise Self-Efficacy Scale ⁶¹	•		•	•
Self-regulation for eating	Three Factor Eating Questionnaire (TFEQ-R18) ⁶²	•		•	•
Sleep	Pittsburgh Sleep Quality Index (PSQI) ⁶³	•		•	•
Motivation	Treatment Self-Regulation Questionnaire (TSRQ) ⁶⁴	•		•	•
Mastery for self-monitoring ^b	Self-Report Habit Index (SRHI) Automaticity subscale ⁶⁵⁻⁶⁶			•	

Construct	Measure or assessment tool	Time Point (months)			
		0	1	3	6
Self-efficacy for self-monitoring ^b	Adapted from Bandura's self-efficacy measure ⁶⁷ to assess self-efficacy for self-monitoring diet, steps, and weight	•	•		
Outcome expectations/realizations	Outcome Expectations ⁶⁸		•		•
Confidence in participating fully	Investigator-designed 1-item measure to capture confidence in participating in weight loss intervention over next 6 months		•		
Health literacy	Newest Vital Sign (NVS) ⁵⁶ via interview	•			
Weight bias internalization	Weight Bias Internalization Scale (WBIS) ⁶⁹	•			
Stress	Perceived Stress Scale (PSS-10) ⁷⁰	•			
Negative life events	Occurrence of negative life events over past 12 months	•			
Stages of change	Stages of change questionnaire in weight management (S-Weight) ⁷¹	•			
Social support	Social Support for Diet & Exercise ⁷²	•			

^aThis outcome will be collected only in the conditions that were asked to track steps (conditions 3, 4, 7, 8).

^bAt the 1-month assessment, these measures will be specific to what domain is being self-monitored (i.e., diet, steps, weight). Only participants in the conditions that are asked to track a given domain will be administered those measures.

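### Does dropping dietary recalls below 800 kcal wrongly shrink the diet-tracking effect on caloric intake?

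*Protocol*

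**What the plan says.** Caloric intake is measured with the ASA24 web tool in "four 24-hour dietary recalls, including two at baseline and two at 6 months". On day type the Protocol says "At both time points, we will request one weekday recall and one weekend day recall". Section 3.8.2 then sets the lower exclusion limit: "We will exclude from our analyses any recalls with outliers of daily caloric intake reported as a minimum of <800 kcal for everyone". The upper limits differ by sex (4400 kcal for women, 5700 kcal for men), and the limits are described as being "in accordance with ASA24 recommended procedures". The score at a time point is the mean of the two recalls, but "if only one recall is available at a given time point, we will use that" value. The outcome is secondary: "Secondary outcomes include the following: 6-month change in caloric intake".

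The same section uses 800 kcal once more, for engagement with the Fitbit food log: "For self-monitoring of diet, we will count days as valid if they have" at least 800 kcal recorded. Section 3.6 sets the minimum daily calorie goal at 1200 kcal for women and 1500 kcal for men. Sections 3.10 and 3.11 refer power and statistical analysis to a separate SAP, which is not examined here.

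**The concern.** The rule selects on the value of the outcome, after randomisation, at the end of the scale toward which the diet component pushes. Suppose a participant truly ate 700 and 1300 kcal on the two recall days. The mean is 1000, but the rule drops the 700 and scores 1300. If this happens more often with diet tracking than without, the difference between the levels shrinks. Nothing in Section 3.8.2 separates a true low day from an unfinished report. The fallback also lets a weekday stand in for a weekend day, or the reverse. At stake is the secondary outcome closest to the diet component: a small effect on intake might be partly produced by the cut-off.

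**Working it through.** The Protocol gives no mean, SD, expected effect or expected share of low recalls for caloric intake, so there is no figure to reproduce. The direction and size were checked by simulation.

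**From the Protocol:** limits of 800, 4400 (women) and 5700 (men) kcal; two recalls at each of two time points; mean of the kept recalls, or the single one kept; 176 participants, so 176/2 = 88 per level of diet tracking.

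**Assumed:** baseline mean 2000 kcal; 6-month means 1500 (tracking) and 1800 (no tracking), a true effect of -300; 70% women, male/female intake ratio 1.25; between-person CV 15% to 25%; within-person day-to-day CV 20% to 40%; lognormal intake.

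**Formulas:** change = mean of kept 6-month recalls minus mean of kept baseline recalls. Effect = mean change with tracking minus mean change without. Loss = 300 minus the size of the scored effect.

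**1. Every low recall is genuine**

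| Within-person CV | Scored effect (kcal) | Loss (kcal) | Loss/300 |
|---|---|---|---|
| 20% | -295 | 5 | 2% |
| 25% | -288 | 12 | 4% |
| 30% | -279 | 21 | 7% |
| 35% | -266 | 34 | 11% |
| 40% | -249 | 51 | 17% |

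The loss must be compared with the standard error from the same CV. With 88 per level and no dropout, the SE is 84 kcal at CV 30% and 107 kcal at CV 40%. That gives 21/84 = 0.25 and 51/107 = 0.48 SE. Dividing the CV-40% loss by the CV-30% error (51/84 = 0.61) mixes two settings and overstates the effect.

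**2. Some low recalls are incomplete reports** (CV 30%, true effect -300; incomplete reports drawn uniformly between 300 and 800 kcal; 5% at baseline in the unequal cases)

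| Incomplete, tracking / no tracking | Stated rule | Keep all recalls |
|---|---|---|
| 5% / 5% | -279 | -286 |
| 10% / 10% | -278 | -269 |
| 5% / 10% | -279 | -223 |
| 10% / 5% | -281 | -334 |

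The rule misses by 19 to 22 kcal throughout. Keeping everything misses by 14 to 77 kcal, in either direction.

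**3. No true effect.** With unequal incomplete reporting, keeping all recalls gives about +64 or -60 kcal, depending on which level has more. The rule gives about 0.

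**4. Day type.** With weekend intake assumed 20% above weekday and CV 30%, a recall-level mixed model with a weekday/weekend term gives -274 on the kept recalls. The Protocol's scoring gives -273. Letting one day type stand in for the other therefore adds no material bias.

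**5. The calorie goals.** A day below 800 kcal lies at least (1200 - 800)/1200 = 33% under the lowest goal that can be assigned to a woman, and (1500 - 800)/1500 = 47% under the lowest for a man. Such days can be real, but they are not what the component asks for.

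**The case for a change.** The strongest reply is that the attenuation is real whenever low days are genuine, and that it may exceed the first table. A wider set of assumptions (baseline mean 1900 to 2100; 6-month means 1300 to 1700 with tracking and 1600 to 1900 without; between-person SD 300 to 400; day-to-day SD 500 to 800; normal or lognormal days) moved the effect toward zero in all 24 scenarios with a true effect, by 6% to 48%. In that set, with equal incomplete reporting, keeping all recalls came closer to the truth: -193 against -160 at 5%, and -186 against -154 at 10%, for a true -199. The incomplete reports in the second table also all fall below 800 kcal, so the rule removes every one by construction.

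All of this stands as arithmetic. It does not show that the rule is wrong. The 48% case needs 33.8% of recalls in the tracking half to fall below 800 kcal and all of them to be true, which nothing in the Protocol supports. Under the same wide assumptions the rule is nearer the truth when incomplete reporting is unequal: -168 against -245, and -144 against -134, for a true -199. There is no bias under the null. Which choice is better depends on how many low recalls are genuine, and that is unknown.

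A comparison analysis that keeps all recalls, with counts of exclusions by condition, would be informative. That is analysis detail a protocol commonly leaves to its SAP, as Sections 3.10 and 3.11 do here.

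**Conclusion.** The concern does not hold. The exclusion limits are stated in advance, apply alike to every condition and to both time points, and are attributed to the recall tool's recommended procedures (a source that cannot be checked here). The 800 kcal limit for food-log days concerns a different measure and is consistent with this one.

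If every recall below 800 kcal were genuine, a -300 kcal effect would lose roughly 5 to 51 kcal under the main assumptions, at most about half a standard error, and more under the wider ones. If some are incomplete, the rule is often the safer choice, and it creates no effect where none exists. All sizes rest on assumed intake means and spreads, because the Protocol gives none. The primary outcome, weight change at 6 months, is not touched. No contradiction, error or badly fixed rule has been shown.
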